- 1. Evaluate impact of OAB on quality of life using the incontinence impact questionnaire
- 2. Compare the number of voids per 24-hour periods
- 3. Compare the number of nighttime voids
- 4. Compare the number of incontinence episodes

Study Design and Methods:

This will be a randomized study of patients with overactive bladder not naive to behavioral therapy and/or pharmacotherapy (or unable to tolerate or with contraindications to pharmacotherapy) with or without urge incontinence recruited through the outpatient offices of the Division of Urogynecology at Women and Infants Hospital and University of Pittsburgh Medical Center Magee-Womens Hospital. The patients will be randomized to receiving unilateral or bilateral PTNS for 30 minutes weekly for a total of 12 weeks. Though we considered the use of a sham needle to decrease participants' bias in reporting their results, we have elected not to use a sham needle. Since all participants will be naïve to PTNS, they are unable to gauge the amount of improvement they should have and therefore we can expect reported improvement to be accurate.

Participants will be asked to complete a 2-day bladder diary at baseline and weekly as per routine PTNS care. Participants will also be asked to fill out a validated OAB symptom severity questionnaire (OAB-q) and the incontinence impact questionnaire (IIQ-7) at baseline (+/- 1 week), four weeks (+/- 1 week), eight weeks (+/- 1 week) and twelve weeks (+/- 1 week).

Our primary outcome will be the improvement in symptom severity as measured by the OAB-q score.

Secondary outcomes will include change in the number of daily voids, change in nocturia or night time voids, change in number of incontinence episodes as measured by the bladder diary and, impact in quality of life as demonstrated by change in score of the incontinence impact questionnaire, IIQ-7.

All questionnaires collected from participants will be labeled with a unique study number and any participant identifiers on the questionnaires or voiding diary will be redacted prior to saving in a research folder in a locked drawer.

Inclusion criteria

Female patients over the age of 18 who have previously tried and failed, or were unable to tolerate, behavioral therapy. Patients will have to consent to participate in the study. Patients on pharmacologic therapy at the time of recruitment will continue their treatment.

Exclusion criteria

- 1. Pregnant patients

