- 2. Patients with pacemakers of implantable defibrillators
- 3. Patients with neurogenic bladder
- 4. Patients who have received Botox or have an implant for sacral nerve stimulation
- 5. Patients with uncontrolled bleeding disorder
- 6. Patients with unhealed ulcers or with leg edema surrounding medial malleolus

Rationale for exclusion criteria

PTNS is an approved procedure that was not previously studied in the pregnant population therefore we will exclude pregnant patients from this study. PTNS is the electrical stimulation of the tibial nerve through a needle and therefore it is unclear how this stimulation would interact with a pacemaker or implantable defibrillator.

While patients with neurogenic bladder may have overactive bladder, the pathophysiology of their urinary frequency and incontinence is different therefore including them in this particular study has the potential to confuse the study results. Botox and Interstim (implantable sacral nerve stimulator) are advanced overactive bladder therapies and are generally offered to those who have failed pharmacotherapy and PTNS and therefore PTNS is unlikely to be effective in participants that have failed more advanced therapies. A needle is inserted through the skin for PTNS and thus PTNS conjures a potential for bleeding. Therefore, those with bleeding disorders will be excluded. Electrical stimulation is sent to the tibial nerve through a needle and therefore leg ulcers and edema can potentially alter the stimulation received by the nerve.

Sample Size calculations

Based on the SUmiT trial results, we expect a decrease in OAB symptom severity of 36.7 with a standard deviation of 21.5 in the unilateral PTNS group. If we estimate that the bilateral PTNS group will show at least 50 % improvement from the unilateral, then we should see an average decrease in in symptom severity of 55 in the bilateral PTNS group.

Our sample size estimate based on 5% significance and 80 % power with a standard deviation of 21.5 will be: 23 per group for a total of 46 participants.

If we expect an attrition rate of about 10%, our goal is therefore to recruit a total of 50 participants with 25 participants in each arm.

Statistical Analysis

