Descriptive statistics will be used to assess the balance of baseline characteristics between randomization groups: unilateral and bilateral PTNS groups. The primary analysis will be intent-to-treat. At baseline, for both treatment groups, the Wilcoxon-rank sum test will be used for all continuous variables and Fisher's exact test for all categorical variables. For the analysis of primary and secondary outcomes, we will compare the last measurement to the baseline measurement within and between treatment groups in OABq score, IIQ-7, daily number of voids, number of nighttime voids, and number of incontinence episodes between the unilateral and bilateral PTNS groups using a pairwise t-test (using a Bonferroni adjustment). These comparisons will result in three sub-analyses: the changes of the primary and secondary outcomes within the unilateral PTNS group, within the bilateral PTNS group, and between the groups (taking the differences between the baseline and last measurement between the groups).

Recruitment and enrollment

Patients with overactive bladder or urge urinary incontinence who have failed behavioral or pharmacologic therapy will have all advanced therapy options presented to them as part of their clinical care by their physician. Those who choose to have PTNS will be approached about the study either by the physician or the research coordinator. If the patient meets eligibility and wishes to participate, they will be consented. In addition, patients who present for their first PTNS visit but were not previously approached about this study will be asked about participating in the study and consented if they are willing

Randomization

Randomization has been performed by a member of the staff at Women and Infants Hospital not part of the research team. Randomization has been concealed in opaque envelopes. Assignment of the randomization envelope to each subject will occur after the patient has signed consent.

Intervention

There will be 12 weekly PTNS treatments of 30 minutes. At the first visit, the participant will complete the OAB questionnaire and the incontinence impact questionnaire. This will be repeated at weeks 4, 8 and 12.

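### The between-arm test is an ambiguously named t-test on unadjusted change; adjusting for the baseline OAB-q already collected would usually narrow the interval at almost no cost

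*Combined protocol and SAP*

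**What the plan says.** In the protocol's Statistical Analysis section, the rule for all outcomes is that "we will compare the last measurement to the baseline measurement within and between treatment groups". The comparison is made "between the unilateral and bilateral PTNS groups using a pairwise t-test (using a Bonferroni adjustment"). Three sub-analyses follow: change within the unilateral arm, change within the bilateral arm, and a between-arm contrast obtained by "taking the differences between the baseline and last measurement between the groups". No ANCOVA, regression or other covariate adjustment appears anywhere in the document.

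The baseline value is available. Study Design and Methods has participants complete "a validated OAB symptom severity questionnaire (OAB-q) and the incontinence impact questionnaire (IIQ-7) at baseline" and again at weeks 4, 8 and 12. Apart from the subtraction, baseline data serve only to describe balance between the arms, with Wilcoxon rank-sum and Fisher tests.

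The Sample Size calculations section states: "Our sample size estimate based on 5% significance and 80 % power with a standard deviation of 21.5 will be: 23 per group". The expected mean decreases are 36.7 (unilateral) and 55 (bilateral).

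**The concern.** There are two linked problems.

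**The test is not identified.** A paired t-test suits change within one arm. It cannot compare two independent arms. The word pairwise, next to Bonferroni, can also mean a set of contrasts. The reader has to infer the primary test from the sample size.

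**Baseline information is left unused.** Subtracting baseline fixes its coefficient at 1. ANCOVA estimates that coefficient, which usually leaves less residual variance. The trial is small, and 23 per arm is the smallest number that reaches 80% power for the planned test, so precision matters. In addition, if the arms differ at baseline by chance, the unadjusted estimate moves with that difference. The planned balance tests may reveal a gap but do not correct for it.

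The trial also has no sham needle, so participants can know their arm. Fixing the test and the covariate in advance removes a choice that could otherwise be made after the data are seen.

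**Working it through.** **Inputs from the protocol (Sample Size calculations).** Difference D = 55 − 36.7 = 18.3; SD 21.5, read as the SD of change; n = 23 per arm; alpha 0.05. Sidedness is not stated. Two-sided is assumed, because a one-sided calculation gives about 18 per group.

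**Inputs assumed.** The protocol gives neither the correlation rho between baseline and last measurement nor separate SDs. The range taken is rho 0.3 to 0.9, with k = follow-up SD / baseline SD at 0.8, 1.0 and 1.2. The change SD is held at 21.5 throughout.

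**1. The plan's own figure.** For an independent two-sample t-test on change:

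- SE = 21.5 × √(2/23) = 6.34
- Noncentrality = 18.3 / 6.34 = 2.89, with 44 df
- Power = 80.6% (22 per arm gives 78.8%)
- 95% CI half-width = 2.015 × 6.34 = 12.8 points

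So 23 per group reproduces exactly with this test.

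**2. ANCOVA.** The ratio of residual variance to change-score variance is

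k²(1 − rho²) / (1 + k² − 2·rho·k), which equals (1 + rho)/2 when k = 1.

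Power uses 43 df and averages over chance baseline imbalance. The expected half-width uses a variance inflation of 1 + 1/42. For example, with k = 1 and rho = 0.5, the residual SD is 21.5 × √0.75 = 18.62, and the half-width is 2.017 × 18.62 × √((2/23)(1 + 1/42)) = 11.2.

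| rho | 0.3 | 0.5 | 0.7 | 0.8 | 0.9 |
|---|---|---|---|---|---|
| Variance ratio, k = 1 | 0.65 | 0.75 | 0.85 | 0.90 | 0.95 |
| Power, k = 1 | 93.3% | 89.6% | 85.6% | 83.6% | 81.6% |
| Half-width, k = 1 | 10.4 | 11.2 | 11.9 | 12.3 | 12.6 |
| Power, k = 1.2 | 89.1% | 84.8% | 81.0% | 79.8% | 80.5% |
| Power, k = 0.8 | 97.6% | 95.8% | 94.0% | 93.6% | 94.7% |

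The unadjusted comparator is 80.6% power and a half-width of 12.8 in every column. The worst cell is k = 1.2 with rho = 0.8, where the ratio is 1.44 × 0.36 / (2.44 − 1.92) = 0.997. There is then nothing to gain, and the spent degree of freedom and the imbalance term cost 0.8 percentage points.

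**3. Simulation check.** With 40,000 trials per cell, ANCOVA power was 0.933, 0.897, 0.855, 0.834 and 0.818 at k = 1. Both estimators were unbiased (mean error within 0.06 points). Type I error was 0.048 to 0.054 for change and 0.049 to 0.052 for ANCOVA. In a separate run of 4,000 trials per correlation at k = 1, the adjusted interval was the narrower one in 99%, 97%, 88% and 56% of trials at rho 0.3, 0.5, 0.7 and 0.9.

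**4. Chance baseline imbalance.** The standard error of the baseline gap is √(2/23) = 0.295 baseline SDs. A gap above 0.25 SD therefore occurs in about 40% of trials of this size, and one above 0.5 SD in about 9%. At k = 1, the baseline SD implied by a change SD of 21.5 is 21.5/√(2(1 − rho)). A gap of one standard error moves the unadjusted estimate by (1 − rho) × baseline SD × 0.295:

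| rho | 0.3 | 0.5 | 0.7 | 0.8 | 0.9 |
|---|---|---|---|---|---|
| Implied baseline SD | 18.2 | 21.5 | 27.8 | 34.0 | 48.1 |
| Shift in estimate (points) | 3.8 | 3.2 | 2.5 | 2.0 | 1.4 |

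**5. Bonferroni.** The protocol gives no divisor. If five outcomes shared alpha (0.01 each, an assumption), unadjusted power would be 58.0%. With ANCOVA at k = 1 it would be 79.5%, 72.3%, 65.5%, 62.4% and 59.4% across the same correlations.

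**The case against.** The strongest reply is that nothing here is an error. A two-sample t-test on change is valid under randomisation, and the sample size and the planned contrast are on the same scale and agree. The three listed sub-analyses make the intended test fairly easy to guess. The gain depends on a correlation and an SD ratio that the documents do not give, and over the grid it runs from +17 percentage points of power to −0.8. Recruiting 25 per arm would give 83.9% power unadjusted if everyone were retained. The undefined Bonferroni divisor could cost more than ANCOVA recovers.

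Much of this stands. It makes the point one of efficiency and clarity, not of bias or of a wrong sample size, and it means the size of the gain cannot be claimed as known. It does not defend the present wording. The possible loss is under one percentage point, while the possible gain exceeds ten in several cells, and the data are collected anyway. The extra two participants per arm are there to cover attrition: 10% off 50 leaves 45, just under the 46 required. The Bonferroni divisor is a separate matter to be settled in its own right; a smaller alpha makes precision more valuable.

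One further caution is sound. The protocol says randomisation has already been performed and does not report enrolment status, so the primary analysis should change only while outcomes by arm remain unseen.

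**Conclusion.** The concern holds, as a recommended improvement. The between-arm test should be named, whatever the correlation. Adjustment for baseline OAB-q is the better primary analysis in most of the plausible range. With equal SDs the half-width shrinks by about 18% at rho 0.3, 12% at 0.5, 7% at 0.7 and 1% at 0.9. The benefit approaches nil when the regression slope of follow-up on baseline is near 1. These figures rest on 21.5 being the SD of change, a two-sided alpha of 0.05, 23 analysed per arm and the assumed correlations and SD ratios. The planned estimate is unbiased and the sample size is not in question.

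**What to change.** In Statistical Analysis, replace the between-arm pairwise t-test for the primary outcome with wording such as:

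> The primary between-arm analysis is an ANCOVA of the last OAB-q symptom severity measurement on treatment arm and baseline OAB-q symptom severity, in the intent-to-treat set. The adjusted mean difference is reported with its 95% confidence interval.

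- State the alpha for this comparison. If Bonferroni applies to it, give the divisor and match the interval to that level.
- Modelling change instead of the last value, with baseline still a covariate, gives the identical treatment estimate. Improvement therefore remains the endpoint.
- Use the same adjustment for IIQ-7, daily voids and nighttime voids. For incontinence episodes, adjust for the baseline count and fix the model in advance, since women are enrolled "with or without urge incontinence recruited through the outpatient offices" and many zeros are possible.
- Keep paired t-tests only to describe change within each arm. If the unadjusted comparison is retained as a sensitivity analysis, call it an independent two-sample t-test on change. If ANCOVA is declined, use that name for the primary test.
- Make and date the amendment before outcomes by arm are examined.

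The cost is a few sentences and one degree of freedom (44 to 43), with no new data, visits or participants. This change does not settle how the last measurement is defined or how missing data are handled.

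### Women come from two hospitals, but no stratification by hospital is described and the between-arm comparison has no hospital term; adding one is a cheap gain in precision

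*Combined protocol and SAP*

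**What the plan says.** Under Study Design and Methods, participants are "recruited through the outpatient offices of the Division of Urogynecology at Women and Infants Hospital and University of Pittsburgh Medical Center Magee-Womens Hospital".

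The Randomization section has three sentences. The first is "Randomization has been performed by a member of the staff at Women and Infants Hospital not part of the research team". The second is "Randomization has been concealed in opaque envelopes". The third is "Assignment of the randomization envelope to each subject will occur after the patient has signed consent". The section does not give the sequence method, blocking or stratification, and does not say how envelopes reach the second hospital.

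The Statistical Analysis section compares OAB-q, IIQ-7 and the diary outcomes "between the unilateral and bilateral PTNS groups using a pairwise t-test (using a Bonferroni adjustment"). It defines the between-arm contrast as "between the groups (taking the differences between the baseline and last measurement between the groups"). It names no hospital term, no other covariate and no summary by hospital.

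**The concern.** Response could plausibly differ between two clinics. The Intervention section has the current raised individually until there is a motor response that the participant finds comfortable. The Inclusion criteria let women already on drug therapy continue it. If mean improvement does differ by hospital, an unadjusted t-test is affected in two ways. The difference between hospitals adds to the residual variance. Any chance imbalance of hospitals across arms also moves the estimate in that particular trial. With about 46 women analysed and 80% planned power, there is little room for avoidable loss.

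**Working it through.** **Inputs from the Sample Size section.** For the unilateral arm, "we expect a decrease in OAB symptom severity of 36.7 with a standard deviation of 21.5 in the unilateral PTNS group". The bilateral arm is expected to fall by 55, so the planned difference is 55 − 36.7 = 18.3. Significance is 5% (taken as two-sided), power 80%, with 23 per arm analysed and 50 recruited, 25 per arm.

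**Assumptions, not in the documents.** The second hospital supplies 40% of women (20 of 50). The SD of 21.5 is within hospital. Mean improvement differs between hospitals by g = 5, 10, 15 or 20 points, equally in both arms.

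**1. The plan's own figure.** The standard error of the arm difference is 21.5 × √(2/23) = 6.34, so the noncentrality is 18.3/6.34 = 2.89 on 44 degrees of freedom. The exact noncentral-t power is 80.6% at 23 per arm and 78.8% at 22. The stated 23 per arm is reproduced.

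**2. Power when hospital is ignored.** The pooled SD is √(21.5² + 0.4 × 0.6 × g²).

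| g | SD | Power of the planned t-test |
|---|---|---|
| 0 | 21.50 | 80.6% |
| 5 | 21.64 | 80.1% |
| 10 | 22.05 | 78.6% |
| 15 | 22.72 | 76.2% |
| 20 | 23.63 | 72.9% |

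**3. Cost of a hospital term if hospitals do not differ.** With hospitals balanced across arms, the degrees of freedom go from 44 to 43 and power from 80.59% to 80.55%.

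**4. Chance imbalance.** If 50 women are allocated 25:25 without regard to hospital, the number of the second hospital's 20 women in one arm is hypergeometric. The chance of a 13:7 or more extreme split, in either direction, is 14.8% (7.4% each way). At 13:7 the hospital's share is 13/25 = 52% of one arm and 7/25 = 28% of the other, a gap of 0.24. At g = 10 the estimate moves by 0.24 × 10 = 2.4 points, which is 2.4/18.3 = 13% of the planned effect and 2.4/6.34 = 0.38 standard errors. This is a tail case: the mean absolute shift under the same assumptions is about 1.1 points.

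**5. Simulation check.** There were 6,000 trials per setting, 23 per arm, hospitals split 23/23 and allocation not stratified.

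| g | Power, t-test | Power, with hospital term | Type I error, t-test |
|---|---|---|---|
| 0 | 80.9% | 79.9% | 4.5% |
| 5 | 79.9% | 79.6% | 4.8% |
| 10 | 79.1% | 80.4% | 5.0% |
| 20 | 71.9% | 79.5% | 5.2% |

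The overall type I error of the planned test stays near 5% throughout. With unstratified allocation the hospital term costs up to about one point of power when hospitals hardly differ, gains about one point at g = 10 and nearly eight at g = 20. With stratified allocation plus the term, power is about 81%, 81%, 82% and 80%.

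**The case against.** The strongest reply is that unstratified 1:1 allocation with an unadjusted t-test is valid. Randomization balances hospital in expectation, the overall error rate is unharmed, and change scores cancel any additive difference between hospitals in baseline severity. Only a difference in response matters, and the documents give no evidence of one. At 5 points or less the loss is negligible. The 21.5 may also already contain some between-hospital variance, in which case planned power is not reduced and a hospital term would improve on it. All of this stands, and it limits the point to precision.

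A reader might go further in several ways that the text does not support:

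- **One shared list with no split by hospital.** The Randomization section is silent. Separate sets per hospital are neither described nor ruled out, and 25 per arm is a recruitment goal, not a description of a list.
- **Staff may take any envelope.** No order of use is stated, but that is missing detail, not permission. Opaque envelopes, preparation outside the research team and assignment after consent are stated safeguards.
- **Operators differ between hospitals.** The documents say where women are recruited. They do not say where, or by whom, treatment is given.
- **Hospital differences bias the comparison.** Imbalance here is a chance event with no preferred direction.

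The silence on stratification does not remove the case for the hospital term. If the lists were stratified, the analysis omits the stratification factor; if they were not, chance imbalance goes uncorrected.

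**Conclusion.** The point holds as a cheap improvement to the analysis, not as a flaw that invalidates it. Two hospitals recruit, no stratification by hospital is described, and the between-arm test ignores hospital. Under the stated assumptions the planned test loses about 0.5, 2, 4 or 8 points of power for differences in response of 5, 10, 15 or 20 points. A 13:7 or worse split at the second hospital, with a 15% chance in either direction, would shift the estimate by at least 2.4 points at a 10-point difference. These sizes depend on the assumed 40% share, the assumed differences and reading 21.5 as a within-hospital SD. The sample size is unaffected.

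**What to change.** In Statistical Analysis, replace the between-arm t-test for OAB-q and each secondary outcome with a linear model for change from baseline to last measurement, with treatment and hospital as terms. Report the arm difference by hospital descriptively, without a test. The within-arm comparisons need not change.

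The protocol says that randomization has already been performed, so changes to the lists may no longer be possible. If any allocations remain to be generated, stratify them by hospital. If none remain, the hospital term still applies.

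The cost is one degree of freedom and, where allocation was not stratified, up to about one point of power if hospitals turn out not to differ. No extra participants or data are needed beyond recording each woman's hospital.
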